PAD-Q Study: Intervention Protocol

Title: To evaluate the effects of personalized dietary advice on improving diet quality and cardiometabolic health

Aim:

To evaluate the effects of personalised dietary advice, tailored to both individual biomarker profiles and a diet quality assessment (assessed using PDQS questionnaire), on improving diet quality and cardiometabolic health, compared with conventional dietary advice, in adults at risk of cardiovascular disease (CVD) on the island of Ireland. These objectives will be assessed in an adult population who are overweight, consume a poor quality diet and who have one or more other risk factors for CVD, on the island of Ireland. This will be a dual-centre study completed at both Queen's University Belfast and University College Dublin. Ethical approval will be obtained separately through the two institutions to cover each recruitment site.

Objectives:

Conduct a 6-month randomized trial among participants at risk of cardiovascular disease (CVD) living in Northern Ireland to examine the effects of a dietary intervention, tailored to both individuals' food biomarker profiles and a diet quality assessment (assessed using PDQS questionnaire) compared with conventional dietary advice.

- **Primary outcome:** change in overall diet quality assessed using the Prime Diet Quality Score (PDQS)
- **Secondary outcomes:** cardiometabolic outcomes (i.e., blood pressure, lipid profile and metabolic markers (e.g. HbA1c), and body composition and body weight), change in biomarkers of diet quality, physical activity levels, habitual dietary intake and demographic/lifestyle information.
- **Exploratory outcome:** changes in gut microbiota compositions and functionality.

Background

A healthy dietary pattern, in which saturated fat, sugar and salt are within recommended ranges and intake of fibre, fruit and vegetables is high, is known to reduce the risk of non-communicable diseases (NCDs)⁽¹⁻⁵⁾. However, global burden of NCDs has continued to rise in recent decades, with

PAD-Q Study: Intervention Protocol

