PAD-Q Study: Intervention Protocol

The Belfast site will recruit n=85 participants according to the inclusion and exclusion criteria. The UCD site will recruit 49 participants.

Those who are interested in taking part in the study after reading the study advertisement will be directed to make contact with the research team. The initial screening process will involve asking participants to complete a screening questionnaire (incorporating all aspects of inclusion/exclusion criteria and collection of contact details) via telephone with the researcher. The screening process will rely on self-reported information obtained from the participant and should take approximately 20-30 minutes to complete. After the telephone call, researchers will review responses within the screening questionnaire and email a link to the Participant Information Sheet to those identified as potentially eligible to take part.

After being given at least 48 hours to read the Participant Information Sheet, the researcher will telephone the participant to discuss the research in further detail and ensure the participant fully understands the study information, implications of involvement and answer any questions they might have. If the participant agrees to participate, they will be invited to complete their consent online and attend the Centre for Public Health for baseline data collection.

Study design and assessments

This is a single-blind randomised controlled parallel group dietary intervention, conducted over 6 months in participants at high risk of cardiovascular disease living on the island of Ireland, to evaluate the efficacy of personalised dietary advice, based on both food biomarkers and a diet quality assessment, in improving diet quality and cardiometabolic outcomes.

Study randomisation will be conducted centrally for both sites (Northern Ireland and Republic of Ireland). Once participants have completed their baseline visit, they will be randomized (randomization scheme generated using www.randomization.com with random block sizes) to either control or intervention group. Participants will be stratified by gender and diet quality. Participants will be unaware of which group they have been randomised to. Control participants will be offered personalised dietary advice at the end of the intervention:

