1) ***Control*** – participants will be given conventional dietary advice based on current regional population dietary recommendations via email to encourage dietary change towards a better quality diet. Participants will be given the dietary advice at baseline (4 messages) and month 3 (4 messages) of the intervention. Control participants will be offered personalised dietary advice at the end of the intervention.

2) ***Personalized dietary advice*** – participants will be encouraged to make dietary change using individualized recommendations incorporating both food biomarkers and diet quality assessment

PAD-Q Study: Intervention Protocol (assessed using PDQS questionnaire). Based on these biomarker data and the diet quality assessment, a system of categorization will be developed and decision trees created to ensure standardized delivery of advice within this intervention arm. In this way, the intervention will be standardised across sites. Relevant behaviour change techniques (BCT), i.e. the BCT framework and the CALOR-E diet and physical activity-specific taxonomy^{11,12} have been integrated into the intervention development. Dietary advice will be delivered via email in both groups.

Participants will commence on the intervention within one month of their baseline visit. This will enable researchers to collect, process and analyse urine samples to help inform the dietary advice given as part of the intervention.

Dietary advice will be delivered via email. Both groups will receive dietary advice at baseline and month 3. Both groups will receive contact from the research team at months 0, 1, 3 and 6 months via email. The control group will be offered personalised dietary advice at the end of the intervention. As such, the frequency and duration of contact will be similar in both groups.

Outcome measures:

Outcomes will be assessed during a study visit at 0, 3, and 6 months and maintenance data will be collected online at 12 months for the primary outcome.

Primary outcome:

- Change in dietary quality assessed by Prime Diet Quality Score (PDQS). This will also be assessed six months after the intervention completes, to determine whether the intervention influences longer term adherence to a better quality diet. (assessed at 0, 3, 6 and 12 months). The 12 month PDQS (6 months post intervention) will be collected online).

Secondary Outcomes:

1. Change in markers of cardiometabolic risk including:

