 - Blood pressure (measured twice from the non-dominant arm, using automated Omron sphygmomanometer, with the participant sitting quietly for at least five minutes. (assessed at 0, 3 and 6 months)).

PAD-Q Study: Intervention Protocol

- Lipid profile (fasting blood samples will be drawn from the antecubital vein and immediately separated into plasma/serum for the proposed assays detailed below. It will be stored at -70°C until analysis (assessed at 0, 3 and 6 months)).
- Other metabolic markers (e.g. HbA1c) (blood sample as above) (assessed at 0, 3 and 6 months).
- Anthropometric measurements (weight (kg), height (m), measured using calibrated scales and stadiometer, respectively, BMI (kg/m²), waist and hip circumference and body composition measured by bioelectrical impedance (Bodystat 1500) (assessed at 0, 3 and 6 months)

2. Demographic/lifestyle information (e.g. alcohol consumption, medication use assessed via questionnaire) (assessed at 0 months; shortened change in medication/lifestyle questionnaire administered at 3 and 6 months).
3. Change in biomarkers of diet quality, including food biomarker-based diet quality score (fasting morning urine sample stored at -70°C until analysis; further details below) (assessed at 0, 3 and 6 months).
4. Physical activity using a 7-day pedometer and Global Physical Activity Questionnaire (GPAQ) (assessed at 0, 3 and 6 months).
5. Habitual dietary intake assessed using the EPIC Food Frequency Questionnaire (assessed at 0, 3 and 6 months).

All questionnaires will be administered via the online survey software Qualtrics.

Exploratory outcome:

- Gut microbiota composition and functionality. Faecal samples will be collected from participants who consent to contribute to this optional element of the study for exploratory analyses. As faecal samples are required from a large proportion (n=70; n=35 in each study arm) of the n=85 participants we intend to recruit at the QUB site, all participants recruited at QUB will be asked to consider consenting to the provision of faecal samples). Participants will be given a faecal sample home collection kit and instructed to collect a sample during the week following the month 0 and month 6 study visits. Full instructions and a postage box will be provided within the faecal sample collection kit so participants can easily return sample to researchers via post.

Laboratory methodology

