The repeated end-point measures generated by the study design will be analyzed with techniques appropriate for longitudinal data using the xt panel study procedures available in Stata release 11 (College Station, TX). Initial examination of the correlation structure of the repeated measures will help guide model fitting. The influence of the dietary intervention under study will be assessed by comparing the means of changes in measurements from baseline to 6 months between the personalised dietary advice and control groups. This difference in means will provide an estimate of the effect of intervention and 95% confidence limits will be calculated to indicate its precision. If appropriate, measurements will be logarithmically transformed prior to analysis and interpretation will be made in ratio terms on the original scale. Compositional analysis of whole metagenome and metatranscriptome datasets will be performed using the read-based bioinformatics analysis suite, including the HUMAnN2158 analysis network¹⁵, MetaPhiAn2 profiler¹⁶ and KneadDATA pipeline, developed in the Huttenhower laboratory at Harvard T.H. Chan School of Public Health. Testing for differences in microbial features between intervention and control groups will be performed with the MaAsLin sparse regression method¹⁷. It is unknown whether men and women respond differently to the same diet, in terms of food biomarker profiles and CHD risk. In previous cohort studies conducted by the research teams, similar associations of various diet quality indices were observed with risk of chronic diseases between men and women¹⁸⁻²¹. In the current study, we consider both men and women, and whenever appropriate, we will perform gender-specific analyses to assess gender difference. We will combine the data of men and women when the test for interactions by gender is not significant, and gender will be adjusted as a covariate.

Process Evaluation

A process evaluation will be conducted at the end of the 6-month study to help elucidate if, how and why the intervention worked. A process evaluation framework for the PAD-Q trial has been developed based on both the Medical Research Council guidance²² and RE-AIM framework²³.

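### Site is neither a randomisation stratum nor a model covariate in this two-centre trial, and the diet-quality stratum is left out of the analysis: a modest, avoidable loss of precision, not a bias

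*Combined protocol and SAP*

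**What the plan says.** The Aim section states: "This will be a dual-centre study completed at both Queen's University Belfast and University College Dublin". The site targets are under Recruitment: "The Belfast site will recruit n=85 participants according to the inclusion and exclusion criteria. The UCD site will recruit 49 participants".

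On allocation, Study design and assessments says: "Study randomisation will be conducted centrally for both sites". It uses random block sizes, and it adds: "Participants will be stratified by gender and diet quality". The number of diet-quality levels is not given.

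Statistical analysis compares mean changes from baseline to 6 months between the arms, using Stata's panel procedures. The one adjustment it names is for gender: when the gender interaction is not significant, men and women are pooled and "gender will be adjusted as a covariate".

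No section uses site as a stratum, fixed or random effect, covariate or interaction term. The remark about examining correlation structure concerns repeated measures within a participant, not clustering by site. Two further statements bear on the point. The control arm receives "conventional dietary advice based on current regional population dietary recommendations". The optional faecal sub-study is drawn from Belfast only and needs "n=70; n=35 in each study arm".

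**The concern.** Central randomisation balances the arms overall and, here, within gender and diet-quality strata. It does not by itself balance them within a site, so by chance one arm can hold more Belfast participants than the other. If participants at the two sites change by different amounts over 6 months, an unadjusted comparison absorbs part of that difference, and the between-site variation stays in the error term.

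A related gap concerns diet quality. Stratifying on a factor buys precision only if the analysis uses it; leaving it out of the model gives up part of that benefit. It also leaves the choice of covariates open until after the data are seen, when adding site or diet quality would look post hoc.

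What is at stake is the width of the confidence intervals, mainly for secondary outcomes powered at about 80%, and how well a site-adjusted result would stand up to challenge.

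**Working it through.** **Inputs from the protocol.** Participants and Recruitment: 134 in total, Belfast 85, UCD 49. Power: 60 per arm analysed; PDQS difference 5, SD 2.3; diastolic blood pressure (DBP) difference 4.5 mmHg, SD of change 9 mmHg; 5% level (taken as two-sided; the document does not say); about 10% drop-out.

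**Assumed.** Equal allocation, 67 per arm. A site difference in mean change of *f* within-site SDs, with *f* = 0.1, 0.3 and 0.5.

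**1. The plan's own figures.**
- Sample size: 120/0.9 = 133.3, rounded up to 134. Reproduced.
- DBP: 4.5/9 = 0.5; 0.5 × √(60/2) = 2.739. Normal approximation: Φ(2.739 − 1.960) = 78.2%. By t-test, 77.5%. Both are slightly under the stated 80%.
- PDQS: 5/2.3 = 2.17; 2.17 × √30 = 11.9, so power is about 100%, which agrees with the stated figure of over 90%.

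**2. Chance imbalance by site.** If allocation ignores site, the Belfast count in one arm is hypergeometric (134 in total, 85 Belfast, 67 drawn).
- Mean: 67 × 85/134 = 42.5.
- Variance: 67 × (85/134) × (49/134) × (67/133) = 7.83, so SD = 2.80.
- Because 85 is odd, the two Belfast arms must differ by an odd number. P(differ by 9 or more) = 15.1%; P(11 or more) = 7.2%.

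A simulation of blocks within four gender-by-diet-quality strata (block sizes 2, 4 and 6 and equal strata assumed; 20,000 runs) agrees in scale. The chance that the UCD share differs between arms by 10 percentage points or more is 24%. It falls to about 0% once site is a stratum.

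**3. Variance removed by adjusting for site.** Let w = (85/134) × (49/134) = 0.232. Total variance = within-site variance × (1 + w*f*²), so the share of total variance removed is 1 − 1/(1 + w*f*²). Taking 9 mmHg as the total SD, the adjusted SD is 9/√(1 + w*f*²).

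| *f* | 1 + w*f*² | Share of total variance removed | Adjusted SD (mmHg) | Site difference in mean DBP change (mmHg) | DBP power, t-test, 60 per arm |
|---|---|---|---|---|---|
| 0 | 1 | 0% | 9.00 | 0 | 77.5% |
| 0.1 | 1.0023 | 0.2% | 8.99 | 0.9 | 77.6% |
| 0.3 | 1.0209 | 2.0% | 8.91 | 2.7 | 78.4% |
| 0.5 | 1.0580 | 5.5% | 8.75 | 4.4 | 79.8% |

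If 9 mmHg is instead the within-site SD, adjusted power stays at 77.5% and unadjusted power falls to 77.4%, 76.7% and 75.2%.

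**4. Shift from a poor draw.** With Belfast arms of 47 and 38, the Belfast share differs by 9/67 = 0.134. Multiplying by the site differences in the table gives a shift of 0.12, 0.36 or 0.59 mmHg in the unadjusted DBP contrast, against an assumed effect of 4.5. For PDQS (SD 2.3, same method) the shift is 0.03, 0.09 or 0.15 points, against 5.

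**5. Primary outcome.** At *f* = 0.5, if 2.3 is the within-site SD, the unadjusted PDQS SD is 2.3 × √1.058 = 2.37, and power is still about 100%. The 2.3 is given as an SD of PDQS, not of its change. If the SD of change were 2.3 × √2 = 3.25, the standardised difference would be 1.54 and power still about 100%.

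**The case against.** The strongest case against is that the contrast is in change from baseline, so stable differences between sites in population, device or staff largely cancel within each participant. A 0.5 SD site difference would mean a DBP change differing by 4.4 mmHg between sites, about the size of the assumed treatment effect, and nothing in the documents supports that. At 0.1 to 0.3 SD the gain is under one percentage point of power. This stands, and it is why the point is modest.

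Four stronger readings are tempting, and the documents do not support them.

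- **Bias.** Chance imbalance under randomisation is not systematic bias, and the overall test remains valid.
- **Different measuring teams.** This is only an inference. Participants mentions a research team at Belfast, but Project timetable gives all data collection to a Research Fellow and a PhD student. The devices are specified once for the whole trial, and the primary outcome comes from an online questionnaire.
- **Control advice differing by region.** The word regional makes this possible, but no section shows that the two regions' recommendations differ. If they did, the result would be a treatment-by-site interaction, which a site main effect would not remove.
- **A threatened faecal sub-study.** The chance that a Belfast arm has fewer than 35 participants is only 0.4%. An arm of 38 would need 35/38 = 92% uptake, but an even split with 10% drop-out already needs 70/(85 × 0.9) = 70/76.5, also about 92%. Optional consent and attrition are the main constraints. What remains is small: an arm of 38 losing 10% leaves 34.2, just short of 35, if the 35 refers to participants who complete. The comparison is exploratory.

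**Conclusion.** The omission is real: site is not used in the allocation or the analysis, and diet quality is used in the first but not the second. It costs precision and allows chance imbalance; it does not invalidate the trial. The Belfast arms differ by 9 or more with probability 15%. The gain in DBP power from adjusting for site is 0.1, 0.9 or 2.3 percentage points for a site difference in mean change of 0.1, 0.3 or 0.5 SD. The primary PDQS comparison is effectively untouched on the plan's own inputs.

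These sizes rest on 67 per arm randomised, 60 per arm analysed, a two-sided 5% test, 9 mmHg as the total SD of change, and assumed site differences. The gain from adjusting for diet quality cannot be sized, because the documents give neither its levels nor its relation to change. The reason to act is that the correction is almost free and, pre-specified, closes off a later argument about covariates.

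**What to change.** In Statistical analysis, pre-specify site (QUB/UCD), gender and the diet-quality stratum as fixed covariates in the model for every outcome measured at both sites, and state the diet-quality levels used for randomisation. For the Belfast-only microbiota comparison, where site is constant, use gender and the diet-quality stratum only. The cost is one or two sentences and two further model terms (more if diet quality has over two levels); no extra participants are needed.

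If randomisation has not begun, also add site as a stratification factor in the central list. The cost is a regenerated list and twice as many strata, for example 8 instead of 4 if diet quality has two levels, averaging 134/8 ≈ 17 participants each, which small random blocks can carry. Project timetable puts the start of recruitment in September 2021; if randomisation is under way, make the covariate change alone, before the outcome data are analysed.

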All methods utilised are routinely used in the participating laboratories and are performed with careful attention to quality control and with participation in external quality control schemes where available. All laboratory analyses will be conducted blind, i.e., the analyst will not know to which intervention the participant has been assigned.

Biomarkers of cardiometabolic risk:

Serum lipids (total cholesterol, HDL-C, and TG) whole blood HbA1c will be assessed by enzymatic assays (Randox Ltd, Crumlin, NI and Glen Bio, Antrim, NI) on a Randox auto-analysern I-Lab 600 auto-analyzer. LDL-C will be calculated.

Biomarkers of diet quality:

The following biomarkers will be used :

- red meat (methylhistidinescarnosine)
- white meat (guanidoacetate, anserine)
- fruit and vegetables (proline betaine, isothiocyanates, S-methyl-L-cysteine sulfoxide, and tartaric acid)
- wholegrains (alkylresorcinols)
- coffee (phenolic acids, N-methylpyridinium, trigonelline, 2-furoylglycine; SSBs --formate, citrulline, taurine, and isocitrate)
- fish (omega-3 index (20:5n-3 and 22:6n-3; % of total fatty acids).

Others will be added as they emerge in the literature.

Gut microbiome composition and functionality (exploratory):

Faecal samples will be collected via home collection kits, posted back to researchers and stored at Queen's University Belfast in preparation for shipment to US partner laboratories for analyses.

Power

PAD-Q Study: Intervention Protocol

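### Does an open marker list with no stated scoring rule undermine the biomarker-based diet quality score as a secondary outcome?

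*Combined protocol and SAP*

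**What the plan says.** The biomarker outcome is item 3 under Secondary Outcomes: "Change in biomarkers of diet quality, including food biomarker-based diet quality score", measured at 0, 3 and 6 months. That item points forward for detail. The detail, under Laboratory methodology (Biomarkers of diet quality), is a list of markers by food group that the protocol commits to using, followed by "Others will be added as they emerge in the literature". No formula, direction, weight or closing date is given there or under Statistical analysis. The latter says only that mean changes from baseline to 6 months will be compared between arms with 95% confidence limits.

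The primary outcome is the change in PDQS, a questionnaire, and "All questionnaires will be administered via the online survey software Qualtrics". The intervention arm receives "individualized recommendations incorporating both food biomarkers and diet quality assessment", so both PDQS answers and biomarkers feed the advice.

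On masking, Study design and assessments calls the trial single-blind, with participants unaware of their group. Laboratory methodology adds that assay analysts are blind. Nothing is said about whoever builds the score or runs the statistical analysis. The contact schedule is matched: "the frequency and duration of contact will be similar in both groups".

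**The concern.** PDQS rests on participants' own answers, and the intervention arm is coached partly on those answers. Some difference between arms in how diet is reported, as opposed to eaten, is therefore possible. The EPIC food frequency questionnaire has the same weakness. The Background section argues that biomarkers avoid self-report, so a reader would naturally look to the biomarker score to see whether a PDQS gain reflects a change in diet.

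If the markers, directions and weights can be settled after the arms have been compared, agreement between the score and PDQS is weaker evidence than it appears. Blind assay work protects the measured values but not the choice of which values to combine. The timetable gives the message templates, day-to-day running and all data collection to the same two staff roles, and states no masking for them. At stake would be the credibility of one secondary comparison and of any support drawn from it for the primary result.

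**Working it through.** **1. Does the score enter any stated figure?** All the sizing is in the Power section, and none of it uses the score.

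- PDQS: difference 5, SD 2.3, 60 per group. 5 / (2.3 × √(2/60)) = 11.9, so power exceeds 0.999, consistent with the stated figure of over 90%.
- Diastolic pressure: difference 4.5, SD 9, 60 per group. 4.5 / (9 × √(2/60)) = 2.74; 2.74 − 1.96 = 0.78; power = 0.782, against a stated 80%.
- Total: 120 / (1 − 0.10) = 133.3, rounded up to 134; 85 + 49 = 134.

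**2. What is fixed without a score?** Counting the listed markers (reading the run-together red meat entry as two): red meat 2, white meat 2, fruit and vegetables 4, wholegrains 1, coffee 4, sugar-sweetened beverages 4, fish 1. That is about 18 in 7 groups. Because the outcome is change in biomarkers *including* the score, each named marker can be compared by arm at 6 months under the general analysis rule.

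**3. When could results steer the choice?** The timetable puts data analysis in September 2023 to May 2024, about 8 months. No interim analysis is planned. Staff handle some individual urine results earlier, because the month after baseline is used to "collect, process and analyse urine samples to help inform the dietary advice given as part of the intervention", but no summary by arm is scheduled before the analysis phase.

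**4. How large could the effect be?** The documents give no number of added markers and no correlations, so this is an illustration on assumed inputs. Assume no true effect, K equally weighted components always in the score, m optional additions with every subset allowed (2^m versions), and pairwise correlation ρ. For a version with k components, z = (sum of component z-values) / √(k + k(k − 1)ρ). The table gives the percentage of trials in which at least one version passes 1.96, for m = 1 / 3 / 5.

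| Setting | Either direction (nominal 5%) | Favouring intervention only (nominal 2.5%) |
|---|---|---|
| K = 7, ρ = 0 | 6.6 / 11.0 / 16.9 | 3.3 / 5.6 / 8.4 |
| K = 7, ρ = 0.3 | 5.9 / 7.6 / 9.2 | 2.9 / 3.8 / 4.6 |
| K = 18, ρ = 0 | 6.1 / 8.7 / 12.1 | about half: 3.0 / 4.4 / 6.0 |
| K = 18, ρ = 0.3 | 5.4 / 6.1 / 6.8 | 2.7 / 3.1 / 3.4 |

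The right-hand column is the relevant one, because false support for a PDQS gain needs a result in the intervention's favour. A rerun of the simulation agreed to within about 0.2 percentage points.

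The table varies only which additions are kept. If an analyst could also choose freely among subsets of the seven base groups, the same model gives 37% (ρ = 0.3) to 55% (ρ = 0) in either direction. So the table does not cap the total freedom. Both sets of figures describe an analyst who searches for a result. Neither estimates what happens when markers are added because new literature supports them.

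**The case for a change.** The strongest case for a change is that it would be cheap. A short dated document fixing the markers and the rule before results are summarised by arm would remove the doubt, and late markers could still be reported as exploratory. Urine collection is already scheduled, so no new samples would be needed. It is also true that blind assays do not protect the scoring step, that the named markers share a list that can grow, and that the unstated weights and directions leave more freedom than the added markers do.

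A related point is that a marker added during recruitment might also feed the advice, which sits uneasily with decision trees meant to "ensure standardized delivery of advice within this intervention arm". The protocol does not say that additions would be used in that way.

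What stands is that the score is under-described and that it would be good practice to write the rule down before analysis. What does not stand is the consequence. No section gives the score the role of confirming PDQS; that is an inference about how readers might use it. The sentence on additions does not mention the score and says nothing about keeping or dropping markers by result. The request is for missing detail to be written out. It neither identifies a method in the plan that would give a wrong answer nor offers a better scoring rule.

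**Conclusion.** No change to the plan follows. The composition, direction and weights of the score are unstated and the list has no closing date. This is a gap in description for one secondary outcome, of a kind that analysts ordinarily fill before comparing arms. Followed as written, the plan yields blind assays in randomised arms, named markers that can be compared individually, and additions driven by outside literature. That is a sound secondary comparison.

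The size is small: nothing changes in the primary outcome, the 134 participants or the power figures. The illustrated rise from 2.5% to between 2.7% and 8.4% requires deliberate selection among one to five added markers. The larger 37% to 55% requires a free search over the base groups as well. The conclusion assumes that the score is defined on scientific grounds before results are viewed by arm. It would weaken if a report rested a claim about true dietary change mainly on a score whose definition could not be dated.

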Based on published US data, with a standard deviation (SD) of PDQS of 2.3, as previously seen¹³, and an assumption of a difference in increase in PDQS of 5 between the personalized dietary advice and control groups, then, if we have 60 participants in each group, the study would have over 90% power to detect this difference in mean PDQS as statistically significant, at the $\alpha=0.05$ level. We will recruit 134 participants in total to allow for approximately 10% drop-out. For the health outcomes, and, based on what was observed in a dietary intervention study on improving diet quality in similar, high CVD risk participants¹⁴, if we have 60 participants in each group, and we assume that (i) the SD of the change in diastolic blood pressure (DBP) is 9 mmHg at the end of the study; (ii) a difference in DBP of 4.5 mmHg between the personalized dietary advice and control groups; then the study would have 80% power to detect, as statistically significant at the 5% level, these differences in mean change between the two groups. We will have similar levels of power (~80%) to detect effect sizes of similar magnitude in total cholesterol, HbA1c, and body weight. The analysis of gut microbiota composition and functionality will be exploratory in nature.

Statistical analysis

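### Is the 80% power stated for diastolic blood pressure wrong on the plan's own inputs?

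*Combined protocol and SAP*

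**What the plan says.** The Power section makes two separate calculations.

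For the primary outcome, PDQS, it takes an SD of 2.3 from published US data, described as the SD of the score. It adds "an assumption of a difference in increase in PDQS of 5 between the personalized dietary advice and control groups", and concludes that 60 per group gives over 90% power at the 0.05 level. It then recruits 134 in total to allow for about 10% drop-out.

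For the health outcomes it works through DBP only. With 60 per group, its assumptions are that "the SD of the change in diastolic blood pressure (DBP) is 9 mmHg at the end of the study" and that the two arms differ by 4.5 mmHg. The power it claims on those inputs is worded as follows: "then the study would have 80% power to detect, as statistically significant at the 5% level". The next sentence describes power for total cholesterol, HbA1c and body weight as similar, and marks that figure as approximately 80%.

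The Statistical analysis section estimates the effect by "comparing the means of changes in measurements from baseline to 6 months between the personalised dietary advice and control groups".

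**The concern.** All the DBP inputs are given together, so any reader can repeat the calculation, and neither of the usual formulas returns 80%. DBP is the only health outcome with explicit inputs, and the power for three other outcomes is described by reference to it. If the figure were materially wrong, the trial's ability to show cardiometabolic benefit would be overstated for all four.

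The PDQS sentence raises a second query. The effect is a difference in increase and the analysis compares mean changes, so the relevant SD is that of the change. The plan labels the DBP figure that way but not the PDQS figure. If 2.3 is the spread of scores at a single visit, it is also the SD of change only when baseline and follow-up scores correlate at 0.5, and the documents state no correlation. What would be at stake is the power for the primary outcome.

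**Working it through.** **Inputs.** From the Power section: n = 60 per group; DBP difference 4.5 mmHg; SD of change 9 mmHg; 5% level; PDQS difference 5; PDQS SD 2.3; drop-out about 10%. Sidedness is not stated. I assume two-sided, because the Statistical analysis section says that "95% confidence limits will be calculated to indicate its precision".

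**Sample size.** 2 × 60 = 120, and 120 / 0.90 = 133.3, rounded up to 134. The plan's total reproduces.

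**DBP power, normal formula.** Power = Φ(difference / SE − 1.960), with SE = SD × √(2/n).
- SE = 9 × √(2/60) = 1.643
- 4.5 / 1.643 = 2.739
- Φ(2.739 − 1.960) = Φ(0.779) = 78.2%

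**DBP power, t test.** The noncentral t distribution with 118 degrees of freedom and the same noncentrality of 2.739 gives 77.5%.

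**One-sided 5%.** This gives 86.3% (normal) or 85.9% (t), so a one-sided reading does not return 80% either.

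**Size of the gap.**
- In power: 80 − 78.2 = 1.8 points (normal), 80 − 77.5 = 2.5 points (t).
- In difference, for exactly 80% with 60 per group: 1.643 × (1.960 + 0.842) = 4.60 mmHg (normal) or 4.64 mmHg (t). That is 0.10 to 0.14 mmHg more than 4.5.
- In participants, for exactly 80% at 4.5 mmHg: 2 × (1.960 + 0.842)² / 0.5² = 62.8, so 63 per group (normal), or 64 (t). That is 3 to 4 more than 60.

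**Rounding of the SD.** The SD is printed as 9, which covers 8.5 to 9.5. At 4.5 mmHg with 60 per group:

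| SD of change (mmHg) | Power, normal | Power, t |
|---|---|---|
| 8.5 | 82.6% | 82.0% |
| 8.7 | 80.9% | 80.2% |
| 9.0 | 78.2% | 77.5% |
| 9.5 | 73.7% | 73.0% |

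The stated 80% lies inside this range.

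**PDQS power.** If 2.3 is the SD of change, SE = 2.3 × √(2/60) = 0.420 and 5 / 0.420 = 11.9, so power is effectively 100%. If 2.3 is instead the SD at each visit, the SD of change is 2.3 × √(2(1 − r)), where r is the correlation between visits. The documents do not give r, so I take limits:
- r = 0: SD of change 3.25, SE 0.594, 5 / 0.594 = 8.42. Power exceeds 99.99%.
- r = −1, the mathematical extreme: SD of change 4.6, SE 0.840, 5 / 0.840 = 5.95. Power still exceeds 99.99%.

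Power for 5 points stays at 90% or more until the SD of change reaches about 8.38 (t), which is 8.38 / 2.3 = 3.6 times the stated SD.

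**The case for a change.** The strongest case for a correction is that the plan itself separates exact from approximate figures. It gives 80% for DBP without qualification and marks the next figure as approximate. The t test, which suits a comparison of means with an estimated SD, gives 77.5%, and no reading of sidedness recovers 80%. A protocol's power statement should be reproducible from its own inputs, and the repair would take only a few words.

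What stands is the arithmetic: with an SD of exactly 9 and a two-sided test, the answer is about 78%. What does not stand is the inference that the plan contains an error. An SD printed as a whole number cannot settle a difference of two points in power. The rounding could run either way, so it neither proves nor disproves 80%. It would also be inconsistent to accept approximately 80% for the other outcomes and reject the DBP figure they refer to, when the only thing missing is a qualifier.

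One could set the 63 or 64 needed against the 67 per group to be recruited and see a conflict with the drop-out allowance. There is none. The DBP statement is made at 60 per group, after drop-out, and the plan never says that the trial was sized on DBP.

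On PDQS, it is true that the plan does not say which SD 2.3 is, and the smallest detectable difference therefore cannot be read from it. But the plan chose to power for a stated 5-point difference, and for that purpose the answer is the same either way.

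**Conclusion.** No change to the plan is needed. The DBP figure is about 78% rounded up to 80%: 1.8 points (normal) to 2.5 points (t) of power, 0.10 to 0.14 mmHg, or 3 to 4 participants per group. That is a loose rounding on a secondary outcome, and correcting it would alter neither the 134 to be recruited, nor the drop-out allowance, the analysis or the reading of any result. The unlabelled PDQS SD is a missing detail without effect, because over 90% power for 5 points holds at every possible correlation between visits.

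The conclusion assumes a two-sided 5% test, equal groups of 60 after drop-out and, for the PDQS limits, the same SD of 2.3 at baseline and follow-up. If the section is being edited for another reason, a qualifier on the DBP figure, the word two-sided and a label for the PDQS SD would help the reader. They are not a reason to amend the plan.
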